If successful, this study will show that statins started prior to anthracyclines preserve LVEF, that statins prevent anthracycline-induced myocardial fibrosis and that the early measurement of myocardial strain or troponin during anthracyclines can identify patients at high risk of a subsequent LVEF decrease.

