#### **Primary End-Point**

**Our primary endpoint will be the proportion of patients in each group that have a decrease of 10% or more in LVEF to <55% from baseline to 12 months after initiation of anthracyclines.**

**Assumptions:** We anticipate that 20% of the patients in the placebo group will reach the primary end-point. This assumption is based on significant prior literature; specifically, Limat *et al.* performed a prospective study where they enrolled patients similar to those proposed in this study (lymphoma receiving anthracycline-based chemotherapy) and performed a baseline measurement of LVEF and a measurement at 1 year. Their primary end-point was a more stringent cut-off than recommended by guidelines or being used in this study, a decrease of >15% in LVEF. They found that 20% of their population had a reduction of >15% in LVEF. Using CMR, two studies have tested the percentage of patients with a significant reduction in LVEF after anthracyclines. In a prospective observational study, Drafts and colleagues found

that 26% of patients decreased their LVEF to <50% and in a prospective randomized study, Bosch and colleagues found that up to 33% of patients decreased their LVEF to <55%. In the single small randomized study which also used 40 mg of atorvastatin with 20 subjects in each arm, there was no decrease in LVEF after anthracyclines among patients on statins. Our base case assumptions are as follows: 20% of the placebo group and 5% of the statin treatment group will meet the primary endpoint and we will be able to enroll 300 patients meeting all inclusion and exclusion criteria. From these, we anticipate a drop-out rate of approximately 10% due to a one year mortality of  $\approx$ 5% and atorvastatin related side-effects in 4% of patients. The remaining 270 patients will provide us with a 98% power to detect a 15% difference in the proportions of those achieving the primary end-point at a one-sided significance level of 0.05. Moreover, we will have a 70% power if the difference in the percentage reaching the primary end-point between groups falls as low as 10%.

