**Statistical Analysis**

**Aim 2a. Assumptions:** In our retrospective clinical study the ECV in healthy age-matched volunteers was 0.28 and was 0.04 lower than in patients treated previously with anthracyclines (0.32, mean difference and SD:  $0.04 \pm 0.05$ ). Based on these data, with 80 patients (40 from each treatment group) we will have 94% power to detect a treatment difference with a two-sided 0.05 significance level. If the actual difference in the ECV between groups is only 0.03 with a SD of 0.05, then we will still have a 75% power to detect a difference between the groups. We are assuming a 10% drop-out for participants in Aim 1. If we assume the same dropout rate for Aim 2, then our final sample size will be 36 per group. A final sample size of 72 will have a 92% power to detect a treatment difference between the means. **Analysis Plan:** The ECV is a unit-less continuous variable. The change in ECV levels from baseline to 6 months will be compared between the statin- and placebo treated groups using a Student *t* test.

**Aim 2b. Analysis plan:** The predictive value of the change in ECV between 0 and 6 months for the occurrence of the primary end-point of Aim 1 (a reduction in LVEF of  $\geq 10\%$  to less than 55% at 12 months) will be determined using a logistic regression model.

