**Statistical Analysis:**

**Aim 3a. Assumptions:** Based on existing literature and our prior data, our assumption is that the decrease in strain after 4 cycles of chemotherapy ( $\approx 200\text{mg}/\text{m}^2$  dose) in the placebo group will be  $9\pm 10\%$ .

**Sample Size and Power:** with a type I error of 0.05, a sample of 270 patients will have a power of 0.99 to detect a statin effect if there is no change in strain in the statin group and a power of 0.96 if the decrease in strain in the statin group is 50% less than that of the placebo group (9% in the placebo group and 4.5% in the statin group). **Analysis Plan:** We will first characterize the distribution and time course of strain and troponin in patients who do or do not reach the primary outcome (significant change in LVEF at 12 months on CMR as defined in Aim 1) using descriptive statistics. As troponin levels at baseline, 4 cycles and their changes do not follow normal distributions, they will be log transformed. To study the effect of statins on the time trends of strain and troponin, we will use a mixed-design ANOVA model to test for differences between the groups while incorporating repeated strain and troponin measurements at 0, 4 cycles and 12 months.

**Aim 3b. Analysis Plan:** The predictive value of the change in strain and/or troponin after 4 cycles for a significant change in LVEF on CMR at 12 months (primary endpoint of Aim 1) will be explored using a mixed design ANOVA model. A multivariable logistic regression model will then be applied, entering strain and troponin as variables. The model may be adjusted for additional key variables such as clinical univariate predictors and change in echocardiographic LVEF.

**Aim 3c. Analysis Plan:** The predictive value of the change in strain and/or troponin after 4 cycles for the change of fibrosis (assessed by ECV) at 6 months will be explored using a mixed-design ANOVA model. The model may be adjusted for additional key variables such as clinical univariate predictors and change in LVEF.

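### The Aim 3b and 3c prediction models do not commit to including randomised arm, so a statin effect on both marker and outcome can pass for marker prediction (Aim 2b: same gap, small effect)

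*Protocol*

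**What the plan says.** **Aim 3b** (Protocol 13.1, Specific Aim 3). The change in strain and/or troponin after 4 cycles is first explored against 12-month AIC by a mixed-design ANOVA whose between-subject factor is not given. Then "A multivariable logistic regression model will then be applied, entering strain and troponin as variables". On covariates: "The model may be adjusted for additional key variables such as clinical univariate predictors and change in echocardiographic LVEF".

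**Aim 3c.** The "change of fibrosis (assessed by ECV) at 6 months will be explored using a mixed-design ANOVA model", again without stated factors and with a similar optional adjustment sentence.

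**Aim 2b** (Specific Aim 2). "The predictive value of the change in ECV between 0 and 6 months for the occurrence of the primary end-point of Aim 1" is assessed by logistic regression, with no covariates named.

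Only Aim 3a, the treatment comparison itself, brings the randomised groups into its model. Nothing restricts or stratifies Aims 2b, 3b or 3c by arm. The SAP covers the primary endpoint and Aims 1a to 1c only, so it does not settle the matter.

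Protocol 1.0 lists among the findings of a successful trial that "the early measurement of myocardial strain or troponin during anthracyclines can identify patients at high risk of a subsequent LVEF decrease".

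**The concern.** The protocol assumes that the statin acts on both sides of these models. It should reduce the fall in strain and the rise in troponin and ECV, and it should reduce AIC. Arm is fixed before either is measured, so it is a common cause of marker and outcome. A pooled model without arm mixes the between-arm contrast with whatever the marker predicts on its own.

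To identify high-risk patients, the marker must say something beyond treatment, which is known to whoever uses the marker. A significant pooled p-value might show only that placebo patients have both worse strain and more AIC. The better the statin works, the larger the distortion.

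**Working it through.** **Inputs (Protocol 13.1)**
- Strain decrease on placebo 9, SD 10; on statin 0 or 4.5 (Aim 3a). Arm shift d = 0.9 or 0.45 SD.
- ECV difference between arms 0.04, or the smaller case: "If the actual difference in the ECV between groups is only 0.03 with a SD of 0.05" (Aim 2a). Arm shift e = 0.8 or 0.6 SD.
- AIC 20% v 5%; also "we will have a 70% power if the difference in the percentage reaching the primary end-point between groups falls as low as 10"%, taken here as 20% v 10% (an assumed split).
- 135 per arm for Aim 3b; 36 per arm after dropout for Aims 2b and 3c.
- Aim 3a is sized "with a type I error of 0.05" without stating sidedness; two-sided is assumed throughout.

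**The plan's own figure.** Aim 3a power is Φ(δ / (σ√(2/n)) − 1.96). For δ = 4.5: 4.5 / (10√(2/135)) = 3.697, and Φ(1.737) = 0.959 (stated 0.96). For δ = 9 it exceeds 0.999 (stated 0.99). The assumed statin effect on the marker is therefore the one used below.

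**Aim 3b by hand, with no association within either arm.** At AIC 20% v 5% the expected events are 135 × 0.25 = 33.75, with 236.25 non-events.
- Placebo share among events: 20/25 = 0.800. Among non-events: 80/175 = 0.457.
- Strain 9 v 0: mean difference between events and non-events = (0.800 − 0.457) × 9 = 3.09 points, although neither arm has any.
- Pooled SD = √(100 + 9²/4) = 10.97.
- z = (3.09 / 10.97) × √(33.75 × 236.25 / 270) = 1.53.
- Rejection = Φ(1.53 − 1.96) + Φ(−1.53 − 1.96) ≈ 0.33.

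The same steps give 0.13 for strain 9 v 4.5. At AIC 20% v 10% (40.5 events; placebo shares 0.667 and 0.471) they give 0.16 and 0.08.

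**Aim 3b by simulation** (6,000 trials, logistic likelihood-ratio test):

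| Strain | AIC | Without arm | With arm | OR per SD, no arm | AUC, no arm |
|---|---|---|---|---|---|
| 9 v 0 | 20 v 5 | 0.344 | 0.057 | 1.34 | 0.583 |
| 9 v 0 | 20 v 10 | 0.161 | 0.049 | 1.18 | 0.547 |
| 9 v 4.5 | 20 v 5 | 0.129 | 0.050 | 1.17 | 0.543 |
| 9 v 4.5 | 20 v 10 | 0.076 | 0.050 | 1.09 | 0.525 |

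A separate set of simulations gave 0.325, 0.163, 0.130 and 0.077 without arm. A t test of strain change by AIC status, which is the group-by-time term of a mixed-design ANOVA, gave 0.33 and 0.12 at AIC 20% v 5%. With no statin effect on strain the rate was 0.052, so the inflation comes from arm.

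**Strain and troponin jointly.** The documents give no arm means or SD for troponin. The assumed arm shift is 0, 0.45 or 0.9 SD, uncorrelated with strain within arm (2-df test, 3,000 trials):

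| Strain | AIC | Without arm |
|---|---|---|
| 9 v 0 | 20 v 5 | 0.266, 0.308, 0.427 |
| 9 v 0 | 20 v 10 | 0.125, 0.133, 0.179 |
| 9 v 4.5 | 20 v 5 | 0.102, 0.159, 0.292 |
| 9 v 4.5 | 20 v 10 | 0.068, 0.093, 0.137 |

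With arm: 0.047 to 0.062 throughout.

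**Aim 3c** (36 per arm; linear regression as a stand-in for the ANOVA). Arm alone induces a pooled correlation r = (de/4) / √((1 + d²/4)(1 + e²/4)). For d = 0.9, e = 0.8: 0.18 / √(1.2025 × 1.16) = 0.152. Fisher's z is atanh(0.152) × √69 = 1.28, which gives rejection of about 0.25. Simulation (20,000 trials):

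| Strain | ECV | Without arm | With arm |
|---|---|---|---|
| 9 v 0 | 0.04 | 0.253 | 0.051 |
| 9 v 0 | 0.03 | 0.163 | 0.049 |
| 9 v 4.5 | 0.04 | 0.107 | 0.052 |
| 9 v 4.5 | 0.03 | 0.079 | 0.049 |

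**Aim 2b** (36 per arm, 5,000 trials). Expected events are 36 × 0.25 = 9.0 at AIC 20% v 5% and 36 × 0.30 = 10.8 at 20% v 10%. Without arm, rejection is 0.069 to 0.114 by likelihood ratio and 0.053 to 0.091 by Wald. With arm, by Firth penalised likelihood ratio, it is 0.043 to 0.051. The chance of no statin-arm event is 0.95^36 = 0.16, or 0.90^36 = 0.02.

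**The case against.** **The pooled association is real.** In the mixed trial population, marker and AIC are associated, so rejecting the pooled null is not an error for that null. No passage says that prediction must hold within arm. This is right as far as it goes: the rates above are false-positive rates only for a within-arm question. That question is nevertheless the one that serves the stated goal, since a patient's treatment is known when the marker is read.

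**The wording leaves room for arm.** The adjustment sentence is permissive, and arm would itself be a univariate predictor of AIC. In simulations that added arm only when it was univariately significant, arm entered in 97% to 98% of trials at AIC 20% v 5% and 64% to 66% at 20% v 10%. The marker test then rejected in 4.8% to 6.1%. This works only if the analysts count arm among clinical predictors and choose to adjust, which the text leaves optional.

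**The largest figure is an extreme case.** It needs full protection of strain, the full AIC effect and no within-arm association, whereas the protocol's background expects the markers to predict. With the smaller effects on both sides, Aim 3b rejects in 8%. This stands, and the range is the fair summary.

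**Aim 3c was not tested as planned.** The plan names a mixed-design ANOVA, and the figures come from a linear regression. That also stands; the factors are not stated, so the planned model cannot be reproduced.

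**The stakes are limited.** The analyses are described as exploratory, the primary analysis is untouched, and the Aim 2b excess is small. All true, and reflected in the weight given to the point.

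**Conclusion.** The concern holds. Under the protocol's own assumed statin effects, a marker with no within-arm relation to AIC would be declared predictive in 8% to 34% of trials in Aim 3b (strain alone), against 5% to 6% with arm in the model. For Aim 3c the range is 8% to 25%, subject to the linear-regression stand-in. Aim 2b is modest.

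These figures rest on two-sided 5% tests, normally distributed markers, the assumed 20% v 10% split for the smaller AIC effect, and an assumed shift for troponin. If the statin does not move the marker, there is no inflation.

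The risk is a false significant association, not a convincing prediction tool. The aims are secondary and support no efficacy claim. The change should be made, but it does not bear on the primary result.

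**What to change.** 1. **Aims 3b and 3c:** make randomised arm a mandatory covariate, and state that the marker's predictive value is assessed given arm.
2. **Aim 3c:** replace the under-specified ANOVA by a linear regression of the ECV outcome on marker change and arm.
3. **Interaction:** add marker-by-arm in Aims 3b and 3c as exploratory only. In Aim 3b about 135 × 0.05 = 6.75, roughly 7, statin-arm events are expected at a 5% rate.
4. **Aim 2b:** account for arm by a Firth-penalised or exact logistic fit, or by stratifying on arm, and request no interaction.

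The cost is one degree of freedom per model and a change of wording. Nothing new is collected. Aim 2b loses a little precision and needs the sparse-event method because about 9 events are expected and about 16% of trials would have none on statin (AIC 20% v 5%).

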**Specific Aim 3:**

**Early clinical identification of patients at high risk of AIC.** We will determine whether an early decrease in myocardial strain or an increase in high-sensitivity troponin *during* anthracyclines (after 4 of 8 standard cycles ( $\approx 3$  months)) can predict subsequent development of AIC at 12 months. We will test:

- d. Whether statins, as compared to placebo, prevent the reduction in strain or the increase in troponin throughout the study period (12 months).
- e. Whether a change in troponin, strain, or both at 3 months predicts AIC at 12 months.
- f. Whether a change in troponin, strain, or both at 3 months predicts fibrosis detected by ECV at 6 months.

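### Aim 3c names a mixed-design ANOVA, without factors, a time-by-marker term or treatment arm, for a question that calls for arm-adjusted linear regression

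*Protocol*

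**What the plan says.** Protocol section 13.1, Specific Aim 3, puts the third question as "Whether a change in troponin, strain, or both at 3 months predicts fibrosis detected by ECV at 6 months". The same question is a secondary objective in section 1.3. The Aim 3c analysis plan says that the predictive value of the marker change "for the change of fibrosis (assessed by ECV) at 6 months will be explored using a mixed-design ANOVA model". It adds "The model may be adjusted for additional key variables such as clinical univariate predictors and change in LVEF", and gives no other model.

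The scales of the variables are set elsewhere in section 13.1:

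- **Outcome.** Under Aim 2a, "The ECV is a unit-less continuous variable", and "The change in ECV levels from baseline to 6 months will be compared between the statin- and placebo treated groups". That is two measurements, hence one change, per patient.
- **Predictors.** Strain change is treated as a mean with an SD under Aim 3a. For troponin, "As troponin levels at baseline, 4 cycles and their changes do not follow normal distributions, they will be log transformed". The Aim 3 plan sets no cut-off for either marker.
- **Size.** The ECV sub-study has 80 patients, or 72 (36 per arm) after the assumed 10% drop-out.

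The SAP covers randomization, the primary endpoint and the Aim 1 secondary endpoints. It does not mention Aim 3.

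**The concern.** A mixed-design ANOVA compares categorical groups on a repeatedly measured outcome. That suits Aim 3a, where two arms are compared on strain and troponin at three time points. Aim 3c is a different problem: a continuous predictor and a single continuous change. For its other predictive questions the protocol reaches a regression model (logistic in Aim 2b, and logistic after an ANOVA step in Aim 3b). Aim 3c has no such step.

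Two things are at stake. First, the analyst must decide how the marker enters the model, and could decide after seeing the data. Second, the sub-study pools both arms. If atorvastatin affects both the marker and ECV, as the protocol hypothesizes, the two will be correlated across the pooled sample even if the marker carries no information within an arm. A model without arm would read that as predictive value.

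**Working it through.** Aim 3c states no power or sample size, so it has no figure of its own to reproduce. The neighbouring figures that supply the inputs do reproduce. Aim 2a states 94%, 75% and 92%; a two-sample t test gives 94.2%, 75.5% and 91.7%. Aim 3a states 0.99 and 0.96; the normal approximation gives more than 0.99 and 0.959.

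**1. Does the named model fit?**

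| | Aim 3a | Aim 3b | Aim 3c |
|---|---|---|---|
| Outcome | strain, troponin at 3 times | AIC, binary | ECV change, one per patient |
| Explanatory variable | arm | marker change | marker change, continuous |
| Factors stated | arm and time | none, but AIC status is a natural group | none |
| Regression step | not needed | logistic | none |

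**2. What would make the model usable?** Write ECV at time t (0 = baseline, 1 = 6 months) as a patient effect + b·t + c·t·x, where x is the continuous marker change. Subtracting the two times gives ECV change = b + c·x + error, which is the simple linear regression. On one simulated data set (n = 72, assumed slope and SDs) both fits gave a slope of −0.001292, t = −1.917, p = 0.0593. The relation can be estimated in a repeated-measures frame, but only through the t·x term, which the plan does not state.

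**3. Correlation induced by arm alone.** Inputs from section 13.1:

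- ECV difference 0.04, SD 0.05 (Aim 2a): d = 0.8.
- Strain decrease 9% on placebo and none on statin, SD 10% (Aim 3a; the same SD is assumed in both arms): d = 0.9.
- 36 per arm.

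With equal arms, the correlation of a variable with arm is (d/2)/√(1 + d²/4).

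- ECV: 0.40/√1.16 = 0.371.
- Strain: 0.45/√1.2025 = 0.410.
- With no relation within arms, the pooled correlation has size 0.371 × 0.410 = 0.152.

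For the unadjusted 5% test by Fisher z: atanh(0.152) × √(72 − 3) = 0.1536 × 8.307 = 1.276, and Φ(1.276 − 1.960) = 0.247, with a negligible opposite tail. The test rejects about 25% of the time. A simulation of 20,000 trials gave 25.0% without arm and 4.9% with arm in the model.

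The protocol's smaller effects (ECV 0.03; strain 9% versus 4.5%) give d = 0.6 and 0.45, correlations with arm of 0.287 and 0.219, a pooled correlation of 0.063, and a rejection rate of about 8%.

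**4. Cost if a marker were split.** Assume a median split and a true correlation of 0.30; neither is in the plan. The split scales the correlation by √(2/π) = 0.798, to 0.239.

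- Continuous: atanh(0.30) × 8.307 = 2.571, power Φ(0.611) = 73%.
- Split: atanh(0.239) × 8.307 = 2.028, power Φ(0.068) = 53%.

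At an assumed 0.35 the figures are 86% and 66%.

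**The case against.** The strongest reply is that the plan is loosely worded rather than wrong. ECV is measured twice, so time is available as a within-patient factor, and arm is available as a between-patient factor. The adjustment sentence allows change in LVEF, normally a continuous quantity, so the authors may not have meant a model of categorical terms only. With a time-by-marker term the model gives the regression slope exactly, as step 2 shows. This stands: a reader might infer that the named model cannot estimate the relation, and the documents do not support that.

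Three further inferences also go too far:

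- **That the plan loses power through a median split.** It sets no cut-off for Aim 3. The background section (A.8) mentions thresholds from earlier breast cancer work, but the analysis plan adopts none.
- **That the plan commits to an unadjusted test.** It leaves adjustment open, so the 25% is what happens if arm is left out.
- **That Aim 3b has the same fault.** There too the marker's value "will be explored using a mixed design ANOVA model", but AIC is binary, so comparing marker trajectories by AIC status is coherent, and the logistic model that follows answers the predictive question.

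What the reply does not remove is that the plan states neither the time-by-marker term nor arm, and that its optional adjustment sentence concerns additional covariates, not how the predictor itself enters.

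**Conclusion.** The point holds as a mismatch and under-specification in Aim 3c, of minor severity. The model as named does not answer the question without additions that the plan does not make. If arm were omitted, the chance of a spurious finding for strain would be about 25% on the protocol's main assumed effects and about 8% on its smaller ones, against a nominal 5%. These figures rest on 72 patients, normal data, equal SDs in the two arms, and no marker-ECV relation within arms. No corresponding figure can be given for troponin, because the protocol states no assumed troponin effect. The median-split loss (73% to 53%) only illustrates one route that is left open. The aim is exploratory and secondary and carries no power claim. The primary endpoint, the randomized comparison and the sample size do not depend on it.

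**What to change.** In Aim 3c, replace the mixed-design ANOVA with linear regression of 6-month ECV on baseline ECV, treatment arm, and the 3-month changes in strain and in log troponin as continuous terms. Report slopes with 95% confidence intervals. A repeated-measures model of ECV at 0 and 6 months serves the same purpose if it explicitly includes a time-by-continuous-marker term and allows the change over time to differ by arm. Name any further covariates in advance. Aim 3b needs no change on this ground. The cost is a sentence or two of analysis-plan wording, with no new data, visits or patients.

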### 13.2 Sample Size, Accrual Rate and Study Duration

**Feasibility:** In 2012, there were 412 patients with lymphoma treated with anthracyclines at MGH, DFCI and BWH (110 at MGH and 312 at DFCI and BWH). In the large cohort of lymphoma patients that we reported in our preliminary data, only 8% of patients ( $n=33$ ) were on statins at the time of chemotherapy and would be excluded. Even using the new more expansive cholesterol guidelines and assuming that all the patients who were eligible to receive statins were treated with statins, more than 80% of patients ( $n=330$ ) would be eligible for enrollment annually. In aggregate, less than 30 of the remaining 330 patients would be excluded based on these criteria and this would leave a final total of 300 patients with lymphoma per year that would meet entry criteria and not meet exclusion criteria. Based on prior trials recruited by this group, we anticipate enrollment of 33% of eligible patients ( $\approx 100$  per year, 8 per month); 5-6 patients per month will be enrolled from DFCI/BWH and 2-3 patients per month from the MGH. We expect a total of about 3 years to complete enrollment.

In total 300 patients need to be enrolled.

Accrual Targets
------------------------

Ethnic Category	Sex/Gender			
	Females		Males	Total
Hispanic or Latino	25	+	26	= 51
Not Hispanic or Latino	125	+	124	= 249
Ethnic Category: Total of all subjects	150 (A1)	+	150	= 300
Racial Category				
American Indian or Alaskan Native	0	+	0	= 0
Asian	16	+	15	= 31
Black or African American	14	+	13	= 27
Native Hawaiian or other Pacific Islander	0	+	0	= 0
White	115	+	117	= 232
Racial Category: Total of all subjects	150(A2)	+	150 (B2)	= 300 (C2)

(A1 = A2)

(B1 = B2)

(C1 = C2)

